3.9.4. Abnormal Movement Scales

Extra pyramidal symptoms (EPS) will be evaluated as AEs and also as assessed by abnormal movement scales. Abnormal movement scales will include the following: Abnormal Involuntary Movement Scale (AIMS), Barnes Akathisia Rating Scale (BARS), and Simpson-Angus Scale (SAS).

For all abnormal movement scales, total scores and subscale scores will be summarized by treatment sequence at each visit for the absolute value and for changes from baseline.

Number and percentage of subjects meeting the criteria for treatment emergent Parkinsonism (SAS total score >3), for treatment emergent akathisia (BARS global clinical assessment of akathisia score ≥2), for treatment emergent dyskinesia (AIMS score ≥3 on any of the first 7 items, or a score ≥2 on two or more of any of the first 7 items) at any postbaseline visit will be summarized by treatment sequence.

A listing will be provided for every abnormal movement scale. Listing for treatment emergent EPS will be provided.

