7.2. Subject Exclusion Criteria

Each subject must not have any of the following conditions to be qualified to participate in this study.

- 1. Subject has any finding that, in the view of the Investigator or Medical Monitor, would compromise the safety of the subject or affect their ability to fulfill the protocol visit schedule or visit requirement
- 2. Subject is currently taking medications that are contraindicated with olanzapine use or exhibit drug-interaction potential with olanzapine will be defined and prohibited at the discretion of the Principal Investigator (PI)
- 3. Subject has a positive test for drugs of abuse at study entry
- 4. Subject is pregnant, planning to become pregnant, or breastfeeding during the study

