Abnormal Movement Scales				x				х						X						X								Х		
IWQOL	Х			Х				Х						Х						Х								Х		
EQ-5D	Х			Х				Х						Х						Х								Х		
Cigarette Use	Х			X				Х						х						х								Х		
Emergency Treatment Card ^m	X	Х	х	х	x	х	Х	X	Х	X	X	X	Х	Х	Х	Х	Х	Х	Х	Х	Х	Х	Х	Х	X	Х	X	Х		
Study Drug Dispensation	Х	Х	Х	Х	X	Х	Х	Х	Х	Х	х	х	Х	х	Х	х	Х	х	х	х	х	Х	х	х	х	х	х			
Study Drug Adherence Review ⁿ		Х	х	x	x	х	Х	х	Х	х	x	х	Х	х	X	X	X	X	X	X	X	Х	X	х	X	X	X	Х		

Abbreviations: AE=adverse event; CGI-S=Clinical Global Impression-Severity; ConMed=concomitant medication; C-SSRS=Columbia-Suicide Severity Rating Scale; ECG=electrocardiogram; EOT=End of Treatment; EQ-5D=EuroQOL-5D; IWQOL=Impact of Weight on Quality of Life; PANSS=Positive and Negative Syndrome Scale

^a A visit window of ±2 days is permitted throughout the Treatment Period and the Follow-up Period (Visits 2-30)

^b Visit 1 must occur within 7 days of the EOT Visit (Visit 6) of the antecedent study, ALK3831-A305, and may occur on the same day. Assessments from ALK3831-A305 Visit 6 will constitute the Baseline/Screening assessments for this extension study

^c On Day 3, study staff will contact outpatient subjects by phone to determine if a dose increase to ALKS 3831 15/10 or 20/10 is needed. An Unscheduled Interim Visit will be arranged for subjects requiring a dose adjustment for study drug return and adherence review and study drug dispensation. Any subsequent dose adjustments throughout the study require subjects to come to the site for either a scheduled or unscheduled visit

^d Follow-up Visits (Visits 29 and 30) are not required for subjects who enroll in ALK3831-A308

^e Urine pregnancy test prior to dosing at Visit 1 and at all subsequent specified visits

Protocol ALK3831-A306 v 3.0 (Amendment 2.0)

- ^f Urine drug screen via dipstick prior to dosing on Day 1 for subjects who did not receive a urine drug screen at Visit 6 of the ALK3831-A305 study, or for subjects for whom Visit 1 of this study is not the same day as Visit 6 of the ALK3831-A305 study. Urine drug screen includes opiates, phencyclidine (PCP), amphetamine/methamphetamine, and cocaine
- ^g Vital signs include orthostatic blood pressure and heart rate, respiratory rate, and oral body temperature. Blood pressure, pulse rate, and respiratory rate will be taken after the subject has been supine for 5 minutes and once again after the subject has stood for 2 minutes

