8.3. Study Procedures Descriptions

Details of the study procedures are described below. The overall schedule of assessments is provided in Table 3. Information collected with the following assessments will be carried forward from the antecedent study, ALK3831-A305, for Screening/Baseline: demographics and medical history, vital signs, physical exam, height, body weight and waist circumference, 12-lead ECG, CGI-S, PANSS, and Abnormal Movement Scales.

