3. DATA ANALYSIS

3.1. General Statistical Methodology

Baseline for efficacy or safety analysis is defined as the last non-missing assessment before the first dose of ALKS 3831 in ALK3831-A306 study, and it will be used for all efficacy and safety analysis unless specified otherwise.

Antecedent study baseline, defined as the last non-missing assessment on or before the first dose of study drug during double-blind treatment period in ALK3831-A305 study, may be explored as applicable.

Treatment sequence is defined according to the treatment assignment in antecedent and current studies as ALKS 3831/ALKS 3831 (ALKS 3831 in both ALK3831-A305 study and ALK3831-A306 study), OLZ/ALKS 3831 (olanzapine in ALK3831-A305 study and ALKS 3831 in ALK3831-A306 study), or PBO/ALKS 3831 (placebo in ALK3831-A305 study and ALKS 3831 in ALK3831-A306 study).

In general, descriptive statistics: n, mean (\pm standard deviation [SD]), median, minimum, and maximum, for continuous variables and number and percentage of subjects in each category for categorical variables will be provided.

All statistical tests and confidence intervals (CIs), unless stated otherwise, will be 2-sided and will be set at an alpha level of 0.05.

All source data will be presented as subject data listings.

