3.9.1. Adverse Events

Incidence of treatment emergent AEs will be analyzed as a safety endpoint. Adverse events will be coded by System Organ Class and Preferred Term using the Medical Dictionary for Regulatory Activities (MedDRA[®]) Version 19.0 or higher. The verbatim term will be included in the AE listings.

An AE (coded by preferred term) will be considered as treatment emergent AE (TEAE) if the event is newly occurring or worsening on or after the date of first dose of study drug in this study.

The number and percentage of subjects reporting TEAEs during the treatment period will be presented by treatment sequence and overall for the following categories:

- System organ class and preferred term
- Preferred term, and including the following subset:
 - TEAEs experienced by $\geq 5\%$ of subjects (in any group) System organ class, preferred term, and severity
 - System organ class, preferred term for serious TEAEs
 - System organ class, preferred term, and relationship
 - System organ class, preferred term for study drug related TEAEs
 - System organ class, preferred term, and severity for study drug related TEAEs

If the same preferred term occurred more than once for the same subject, the subject will be counted only once for that preferred term using the most severe and most related occurrence for the summarization by severity and by relationship to the study drug.

In addition, the number and percentage of subjects reporting AEs during the safety follow-up period will be tabulated by the system organ class, preferred term and treatment sequence and overall.

The number and percentage of subjects who have serious adverse events (SAE) and AEs leading to premature discontinuation from the treatment will be summarized by system organ class, preferred term, and treatment sequence and overall.

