3.9.2. Clinical Laboratory Parameters

Laboratory parameters will be presented in conventional (ie, US) units. Only scheduled laboratory parameters will be included in the summaries, unless specified otherwise. All laboratory data, including those collected at unscheduled visits, will be included in the listings.

Laboratory results including baseline and change from baseline for the Safety Population during the treatment period for chemistry and hematology parameters will be summarized by treatment sequence, overall, and by visit.

Clinical laboratory test values, scheduled or unscheduled, will be considered potentially clinically significant (PCS) if they meet PCS criteria listed in [Table 1](#). The number and percentage of subjects who have postbaseline PCS clinical laboratory values will be summarized by treatment sequence and overall. The percentages will be calculated based on the number of subjects with non-PCS baseline value and have at least 1 postbaseline assessment. All PCS values including baseline PCS values will be included in supportive listings.

Shift tables for selected metabolic parameters (glucose, total cholesterol, LDL, HDL, tryglyceride, and HbA1c) and liver function tests will be presented. The criteria are summarized in [Table 2](#), [Table 3](#) and [Table 4](#).

Table 1: Criteria of Potentially Clinically Significant (PCS) Abnormality for Selected Analytes

Parameters	Criteria
Chemistry	
Albumin	<2.5 g/dL
Alkaline Phosphatase (U/L)	$\geq 3 \times \text{ULN}$
Alanine Aminotransferase (U/L)	$\geq 3 \times \text{ULN}$
Aspartate Aminotransferase (U/L)	$\geq 3 \times \text{ULN}$
Bilirubin, Total	$\geq 2.0 \text{ mg/dL}$
Blood Urea Nitrogen	$>30 \text{ mg/dL}$
Cholesterol, Random	$>300 \text{ mg/dL}$
Cholesterol, Fasting	$\geq 240 \text{ mg/dL}$
Cholesterol, HDL Fasting	$\leq 30 \text{ mg/dL}$
Cholesterol, LDL Fasting	$\geq 160 \text{ mg/dL}$
Creatine Kinase (U/L)	$\geq 3 \times \text{ULN}$
Creatinine	$\geq 2.0 \text{ mg/dL}$
Glucose, Random	$<50 \text{ mg/dL}$ or $\geq 200 \text{ mg/dL}$
Glucose, Fasting	$<50 \text{ mg/dL}$ or $\geq 126 \text{ mg/dL}$
Potassium	$<3 \text{ mmol/L}$ or $>5.5 \text{ mmol/L}$
Lactate Dehydrogenase (U/L)	$>3 \times \text{ULN}$
Prolactin (Female)	$>30 \text{ ng/mL}$
Prolactin (Male)	$>20 \text{ ng/mL}$
Sodium	$<130 \text{ mmol/L}$ or $>150 \text{ mmol/L}$
Triglycerides, Fasting (Female)	$\geq 120 \text{ mg/dL}$
Triglycerides, Fasting (Male)	$\geq 160 \text{ mg/dL}$

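### SAP 3.9.4 calls movement-scale cases treatment emergent on an absolute post-baseline score, without requiring the subject to be below the threshold at A306 baseline

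*SAP*

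**What the plan says.** SAP 3.9.4 defines three case counts from the movement scales. The Parkinsonism count begins "Number and percentage of subjects meeting the criteria for treatment emergent Parkinsonism (SAS total score >3". Akathisia is a BARS global score of at least 2. Dyskinesia is an AIMS score of at least 3 on one of items 1 to 7, or at least 2 on two or more of them. All three are counted "at any postbaseline visit will be summarized by treatment sequence". The section gives no condition on the baseline score and no denominator of its own. SAP 3.9 supplies the Safety Population as the general rule for safety endpoints.

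Baseline is set in SAP 3.1: "Baseline for efficacy or safety analysis is defined as the last non-missing assessment before the first dose of ALKS 3831 in ALK3831-A306 study". The values come from the antecedent study. Footnote b to Protocol Table 3 states "Assessments from ALK3831-A305 Visit 6 will constitute the Baseline/Screening assessments for this extension study", and Protocol 8.3 lists what is carried forward, ending with "12-lead ECG, CGI-S, PANSS, and Abnormal Movement Scales".

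Protocol 14.4 promises the number and percentage of subjects with shifts in laboratory parameters and in AIMS, BARS and SAS. The SAP's shift tables (Tables 2 to 4) cover lipids, glucose and HbA1c, and liver tests. SAP section 5 reports no major deviation from the protocol's analyses.

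**The concern.** A count labelled treatment emergent should separate problems that arise on the A306 drug from problems already present on entry. Subjects reach A306 baseline after four weeks on ALKS 3831, olanzapine or placebo, so some may already be over a threshold. No exclusion criterion in Protocol 7.2 names existing extrapyramidal symptoms. The nearest is discretionary: "Subject has any finding that, in the view of the Investigator or Medical Monitor, would compromise the safety of the subject".

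Long-term safety and tolerability is the primary objective, and this is the only summary that turns the scales into a count of cases. If persistent or improving cases enter it, the table does not measure what its label says. Baseline positivity could also differ between the three A305 treatments, in which case the treatment-sequence columns would differ partly for reasons that predate A306.

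**Working it through.** The plan states no extrapyramidal rate, so there is no figure to reproduce. The check sets the rules side by side and then works out what each would count.

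**1. Rules elsewhere in the SAP**

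- Laboratory (3.9.2): "The percentages will be calculated based on the number of subjects with non-PCS baseline value and have at least 1 postbaseline assessment".
- Vital signs (3.9.3.1) and ECG (3.9.3.3): the same denominator, and the numerator is also limited to subjects without the abnormality at baseline.
- Weight (3.9.3.2): Safety Population subjects with a post-baseline value. The criterion is itself a change from baseline.
- Adverse events (3.9.1): "An AE (coded by preferred term) will be considered as treatment emergent AE (TEAE) if the event is newly occurring or worsening". This is the only definition of treatment emergent in the SAP, and it applies to coded events.
- Movement scales (3.9.4): none of these is stated.

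**2. Who is counted under each reading**

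Among subjects with a baseline score who meet a criterion after baseline, let:

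- A = below the threshold at baseline;
- B = over it at baseline and worse afterwards (for example BARS global 2 to 4);
- C = over it at baseline, then unchanged or better but still over (for example SAS 5 to 4).

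| Reading | Numerator |
|---|---|
| 3.9.4 taken literally | A + B + C |
| Adverse-event wording applied to scores | A + B |
| Baseline-negative rule, as for vital signs and ECG | A |

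The literal numerator exceeds the baseline-negative one by B + C. If nobody is over a threshold at baseline, B = C = 0 and the three numerators agree.

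**3. Effect per subject**

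Protocol 14.1 plans approximately 390 subjects, an estimated maximum. With the denominator held at 390, each subject in B or C contributes 1/390 = 0.256, or about 0.26 percentage points, to the overall figure. The contribution is larger if fewer enrol, and larger within a single treatment-sequence column.

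**4. Effect on the percentage**

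The fix changes the denominator too, so B + C alone does not give the change in the percentage. Let p be the share positive at baseline, r the share of those positive again later, and i the new-onset proportion among baseline-negative subjects. If everyone is assessed:

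- literal percentage = p·r + (1 − p)·i
- baseline-negative percentage = i
- difference = p·(r − i)

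The literal figure is therefore too high when r exceeds i. Subjects with no post-baseline scale pull the other way: they stay in the Safety Population denominator but cannot be cases. The scales are scheduled after baseline at Visits 4, 8, 14, 20 and 28 (Weeks 4, 12, 24, 36 and 52). A subject who leaves before Week 4 and does not attend the early-termination visit would have none. The documents give no value for p, r, i or the unassessed share, so any range would only reflect the values chosen.

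**5. Shift summary**

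Most entries in SAP Tables 2 to 4 are one-way counts from a baseline category to a worse category at any later assessment. The 3.9.4 count has no baseline category, so as written it is not a shift. With a baseline-negative condition it would take the same form as those entries.

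**The case against.** The strongest reply is that the words *treatment emergent* already carry a baseline condition, so no programmer would count SAS 5 to 4. That may well be the intent, and the separate specifications and table shells, which were not available, may say so. But the SAP defines the term only for coded adverse events. Carried over to scores, that definition gives A + B, which differs from the rule written for vital signs and ECG. The label therefore does not settle the count.

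Three further points stand and limit the concern:

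- A reader might infer that the percentage has no denominator at all. It has one: SAP 3.9 supplies the Safety Population. What is unstated is whether baseline-positive and unassessed subjects should stay in it.
- A reader might infer that a separate score-level shift table is owed. Protocol 14.4 promises a count of subjects with shifts, not a particular layout. A baseline-negative 3.9.4 count would largely deliver it, and a further table is optional.
- A reader might infer that SAP section 5 is wrong. It denies only major deviations, and the form of one descriptive summary need not be major.

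Extrapyramidal symptoms are also reported as adverse-event subsets (3.9.1.1), by-visit values and changes from baseline, and listings (3.9.4). A persistent case would be visible there.

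**Conclusion.** The concern holds as a fault in a stated rule. Followed literally, SAP 3.9.4 counts persistent or improved baseline-positive subjects as emergent, uses a default denominator that includes subjects who could not be new cases, and leaves the Protocol 14.4 shifts in the movement scales undelivered without comment. It should be corrected, though the harm is limited: the tables are descriptive and other summaries of the same symptoms remain.

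The size is unknown. The numerator error is B + C, at about 0.26 percentage points per subject with 390 in the denominator. A reader might go further and conclude that the reported rates will be inflated. The documents do not support that. They give no baseline scores, they do not show that any subject enters A306 over a threshold, and unassessed subjects in the denominator would lower the percentage. Confidence is high that the condition is missing from the text; nothing here measures its effect.

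**What to change.** In SAP 3.9.4, add for each criterion:

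> The denominator is subjects in the Safety Population with a non-missing baseline score on the scale that does not meet the criterion and at least one post-baseline assessment of that scale. The numerator is those of them who meet the criterion at any post-baseline visit.

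Then state that this count serves as the AIMS, BARS and SAS shift summary of Protocol 14.4, or record the change in SAP section 5. Optionally, add one line for subjects positive at baseline whose worst post-baseline score is higher than baseline, so that group B stays visible.

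The cost is two sentences, one cross-reference and at most one extra table line. The baseline scores are already carried over from A305, so no new data are needed. The small downside is that baseline-positive subjects leave the emergent percentage and appear as cases only in the optional line and the listings.

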3.9.5. Columbia-Suicide Severity Rating Scale (C-SSRS)

The C-SSRS is a questionnaire used to measure the presence and intensity of suicidal ideation and behavior.

Suicidal behavior and suicidal ideation will be summarized for the Safety Population. The number of subjects with suicidal ideation and suicidal behavior will be summarized by treatment sequence when applicable.

Supportive tabular display of subjects with all values will be provided.

Table 8: C-SSRS Categories for Analysis

Category	C-SSRS Item response is “YES”
Suicidal behavior	Preparatory acts or behavior Aborted attempt Interrupted attempt Actual attempt Complete suicide

Suicidal ideation	Wish to be dead Non-specific active suicidal thoughts Active suicidal ideation with any methods (not plan) without intent to act Active suicidal ideation with some intent to act, without specific plan Active suicidal ideation with specific plan and intent
Non-suicidal Self-Injurious Behavior	Non-suicidal Self-Injurious Behavior

3.10. Pharmacokinetic/ Pharmacodynamic Data Analysis

Not applicable.

4. INTERIM ANALYSES

No interim analysis is planned for this study.

5. CHANGES IN CONDUCT OR PLANNED ANALYSES FROM THE PROTOCOL

There are no major deviations from the protocol specified analysis.

6. DEFINITIONS AND CONVENTIONS FOR HANDLING OF THE DATA

Dataset specifications will be provided in a separate document.

6.1. Analysis Visit Windows

Scheduled analysis visits are visits at scheduled timepoints as specified in the protocol ([Table 1 Schedule of Visits and Assessments](#)).

Scheduled analysis visits during the study period will be the same as the nominal visits collected in eCRF. There will be one valid value of assessment kept for each scheduled analysis visit in summary/analysis statistics.

Unscheduled visits are visits with data not collected on the scheduled time point. Unscheduled visits will not be used for by-visit summary/analysis statistics, unless specified otherwise.

All unscheduled visits as collected in eCRF will be included in listings.

Visit Day is calculated as date of visit – date of the first dose of study drug + 1 day.

Last postbaseline values are defined as the last valid postbaseline values collected for each subject during the treatment period.

6.2. Handling of Partial Dates of Concomitant Medication

Partial start dates of prior and concomitant medications will be assumed to be the earliest possible date consistent with the partial date. Partial stop dates of prior and concomitant medications will be assumed to be the latest possible date consistent with the partial date. In the case of completely missing stop date, medication will be assumed to be ongoing.

6.3. Handling of Safety Data

All efforts should be made to obtain the missing information from the investigator. For C-SSRS, vital signs, laboratory testing (chemistry, hematology, urinalysis), and 12-lead ECGs, only observed data will be used for analyses, and missing data will not be imputed.

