7.3. Subject Withdrawal

A subject may be discontinued from the study at any time if the subject, Investigator, or the Sponsor determines that it is not in the best interest of the subject to continue participation. If a subject has an absolute neutrophil count (ANC) $< 1.0 \times 10^3$ per µL or HbA1c $\geq 6.5\%$ at any time during this extension study, the subject will be discontinued from the study. Other reasons for discontinuation include the following:

- AEs
- Lack of Efficacy
- Lost to follow-up
- Withdrawal by subject

- Protocol Deviation (noncompliance with study drug or study procedures)
- Pregnancy
- Study terminated by Sponsor
- Other

If a subject withdraws from the study for any reason, any ongoing AEs will be followed until resolution, until deemed stable by the Investigator, or until the subject is deemed by the Investigator to be lost to follow-up. If, in the opinion of the Investigator, it is necessary to monitor a subject beyond the Safety Follow-up Visit, the Follow-up Period may be extended, as necessary. In such instances, the Sponsor and the Investigator will agree to an acceptable follow-up schedule.

In the event that a subject chooses to withdraw from the study, the Investigator should make a reasonable effort to ascertain the reason(s) for withdrawal, while fully respecting the subject's rights. Enrolled subjects are to be asked to return to the clinic for an Early Termination (ET) Visit and to complete a subsequent Safety Follow-up Period. The ET Visit should be scheduled as close as possible to the subject's last dose and will mimic the assessments scheduled to be conducted at the End of Treatment (EOT) Visit (Visit 28, Table 3). If the subject fails or refuses to return to the study center, an attempt must be made to contact the subject by telephone in order to assess as many safety and efficacy parameters as possible. All data collected over the telephone must be documented and kept in the subject's record.

The Investigator must maintain a record of all subjects who fail to complete the study. The reason for study discontinuation will be documented and entered on the appropriate electronic case report form (eCRF). If a subject is lost to follow-up, a reasonable attempt to contact the subject must be made and documented.

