8.2. Schedule of Visits and Assessments

The schedule of assessments is shown in Table 3.

A visit window of ± 2 days is permitted throughout the Treatment Period and the Follow-up Period (Visits 2-30). For a missed visit, the site should attempt to contact the subject to reschedule.

Premature discontinuation procedures are provided in Section 7.3.

On Day 3, study staff will check in with outpatient subjects by phone to determine if a dose increase to ALKS 3831 15/10 or 20/10 is needed. If, in the opinion of the Investigator, a dose increase is warranted, an Unscheduled Visit will be arranged mid-Week 1. The following procedures will be performed during the Unscheduled Visit: study drug return, adherence review, and study drug dispensation.

Dose adjustments can only occur on-site and require subjects to come to the study center. Throughout the study, subjects requiring dose adjustments between scheduled visits may arrange an Unscheduled Visit (same procedures as mid-Week 1 Unscheduled Visit described above).

Table 3:Schedule of Assessments

												0	pen I	abel	Trea	tmen	t Peri	iod											u	low- 1p riod
Visit ^a	1 ^b	2 [°]	3	4	5	6	7	8	9	10	11	12	13	14	15	16	17	18	19	20	21	22	23	24	25	26	27	28/ ET/ EOT	29 ^d	30
Study week	-	1	2	4	6	8	10	12	14	16	18	20	22	24	26	28	30	32	34	36	38	40	42	44	46	48	50	52	54	56
Informed Consent	х																													
Eligibility Criteria	x																													
Pregnancy Testing ^e	х							Х						Х						Х										
Urine Drug Screen	Х																													
Weight		Х	Х	Х	Х	Х		Х		Х		Х		Х		Х		Х		Х		Х		Х		Х		Х		Х
Waist Circum- ference		Х	х	х	х	Х		Х		Х		Х		Х		Х		Х		Х		Х		Х		Х		Х		X
Vital Signs ^g		Х	Х	Х	Х	X		Х		Х		Х		Х		Х		X		Х		Х		Х		Х		Х		Х
Laboratory Samples ^h				Х				Х						Х						Х								Х		
ECG				Х				Х						Х						Х								Х		
Physical Exam				X				Х						Х						Х								Х		
PANSS ⁱ				Х		Х		Х						Х						Х								Х		
CGI-S				Х		Х		Х		Х		Х		Х		Х		Х		Х		Х		Х		Х		Х		
AE ^j		Х	Х	Х	Х	Х	Х	Х	Х	Х	Х	Х	Х	Х	Х	Х	Х	Х	Х	Х	Х	Х	Х	Х	Х	Х	Х	Х	Х	Х
ConMed ^j		Х	Х	Х	Х	Х	Х	Х	Х	Х	Х	Х	Х	Х	Х	Х	Х	Х	Х	Х	Х	Х	Х	Х	Х	Х	Х	Х	Х	Х
C-SSRS ^k		Х	Х	Х	Х	Х	Х	Х	Х	Х	Х	Х	Х	Х	Х	Х	Х	Х	Х	Х	Х	Х	Х	Х	Х	Х	Х	Х	Х	Х

Table 3:Schedule of Assessments (Continued)

												Ор	en La	abel T	reati	ment	Perio	d											Foll u Per	р
Visit ^a	1 ^b	2°	3	4	5	6	7	8	9	10	11	12	13	14	15	16	17	18	19	20	21	22	23	24	25	26	27	28/ ET/ EOT	29 ^d	30
Study week	-	1	2	4	6	8	10	12	14	16	18	20	22	24	26	28	30	32	34	36	38	40	42	44	46	48	50	52	54	56

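### By-visit HbA1c means omit subjects withdrawn earlier for HbA1c ≥6.5%, and the HbA1c shift table does not fully recover them; the bias is probably modest

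*SAP*

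**What the plan says.** Protocol 7.3 sets the exit rule. If HbA1c is 6.5% or higher "at any time during this extension study, the subject will be discontinued from the study".

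SAP 3.9.2 describes the laboratory means: "Laboratory results including baseline and change from baseline for the Safety Population during the treatment period", for chemistry and hematology, "will be summarized by treatment sequence, overall, and by visit". The same section adds: "Only scheduled laboratory parameters will be included in the summaries, unless specified otherwise". SAP 6.3 says of laboratory tests, among other safety data, that "only observed data will be used for analyses, and missing data will not be imputed". SAP 7 repeats the observed-data rule and keeps unscheduled and repeat measurements out of by-visit tables.

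Protocol Table 3 schedules the row "Laboratory Samples" at Weeks 4, 12, 24, 36 and 52, the last in a column labelled 28/ET/EOT. The early-termination visit "will mimic the assessments scheduled to be conducted at the End of Treatment (EOT) Visit" (Protocol 7.3). For assignment, "Scheduled analysis visits during the study period will be the same as the nominal visits collected in eCRF" (SAP 6.1).

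Other domains are handled differently. Weight, BMI and waist circumference are summarised on both observed and LOCF data (SAP 3.9.3.2). ECG parameters are also summarised at the end of the treatment period (SAP 3.9.3.3). SAP 6.1 defines a last postbaseline value, but the laboratory section does not call for it.

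**The concern.** The variable being averaged decides who stays in the average. A by-visit mean on observed data is unbiased for the whole treated group only if those who have left resemble those who remain. Here one route out is defined by a high value of the variable itself, so the direction of the error is known in advance.

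The study's only objective is long-term safety and tolerability, and the protocol's background presents the product as olanzapine with less weight gain and fewer of the associated metabolic deficits. A reader will use the HbA1c tables to judge that. Nothing in the planned by-visit table tells the reader that high values triggered removal. What is at stake is a small understatement of the later means and, more practically, whether every subject who reached the limit appears in some HbA1c summary.

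**Working it through.** The plan has no figure to reproduce: the approximately 390 subjects are a feasibility number, and no HbA1c distribution is given. The check traces a subject through the rules and then sizes the effect on stated assumptions.

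**1. Trace.** A subject first reaches 6.5% at the scheduled Week 12 sample.
- Weeks 4 and 12: included. The triggering value counts at its own visit. If the trigger came from an unscheduled sample, it would enter no by-visit mean.
- Weeks 24 and 36: absent.
- Week 52: absent if the early-termination sample is kept apart, or represented by an exit value from months earlier if that sample carries the Visit 28/ET/EOT label. The SAP does not say which.

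Each mean from Week 12 on therefore omits those who crossed at an earlier visit, but includes those who first cross at that visit.

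**2. Formula.** All-subject mean − observed mean = p × (mean of removed − mean of retained), where p is the fraction already removed.

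**3. Level of HbA1c.** Simulation at Weeks 4, 12, 24, 36 and 52, starting below 6.5%, with removal after the first value of 6.5% or more. All inputs are assumptions: slope SD 0.15 per year, within-subject SD 0.15, and the baseline mean, SD and yearly drift shown.

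| Baseline mean / SD / drift | Removed before Week 52 | Mean too low, Week 24 | Week 36 | Week 52 |
|---|---|---|---|---|
| 5.4 / 0.30 / +0.1 | 0.3% | 0.001 | 0.001 | 0.002 |
| 5.5 / 0.35 / +0.1 | 1.4% | 0.005 | 0.008 | 0.012 |
| 5.5 / 0.40 / +0.2 | 2.9% | 0.010 | 0.017 | 0.025 |
| 5.6 / 0.45 / +0.2 | 5.9% | 0.021 | 0.034 | 0.049 |

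Of 390 subjects, 0.3% is about 1 (390 × 0.003 = 1.2) and 5.9% is 23 (390 × 0.059 = 23.0). The formula agrees: in the last row 0.049 / 0.059 implies a gap of 0.83 points between removed and retained.

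**4. Change from baseline.** Much of that gap already exists at baseline: a subject going from 6.4% to 6.5% is removed with a change of only 0.1. Over the same ranges of mean, SD and drift, with slope SD 0.1 to 0.3 and within-subject SD 0.12, the Week 52 bias is 0.001 to 0.059 in level but 0.000 to 0.017 in change. A true mean rise of about 0.10 is observed as about 0.09 to 0.10, and one of about 0.20 as about 0.19 to 0.20.

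**5. Glucose.** With an assumed SD of 12 mg/dL and correlation of 0.5 with HbA1c, the four scenarios in step 3 give a Week 52 glucose mean that is 0.05 to 0.66 mg/dL too low. A subject with high fasting glucose but HbA1c below 6.5% is not removed by this rule.

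**6. Do the categorical tables recover the cases?** SAP Table 1 has no HbA1c criterion. All three HbA1c rows of SAP Table 3 start from a baseline below 5.7%. A subject with baseline 5.7–6.4% who reaches 6.5% is in none of them. In the step 4 simulation, 77% to 100% of those who crossed had started at or above 5.7%, so the existing row would show at most 23% of them (100 − 77).

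**7. Does a last-value summary help?** In the same simulation the mean change to the last on-treatment value was within 0.006 points of the true Week 52 change.

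**The case against.** The strongest reply is that the plan does not generally conceal these subjects. Any-postbaseline shifts in fasting glucose are tabulated, including a move from below 126 to 126 mg/dL or more. Fasting glucose of 126 mg/dL or more is a PCS criterion, and PCS analyses use unscheduled values. Clinically significant laboratory values are to be recorded as adverse events, adverse events leading to discontinuation are tabulated, and all values are listed. This stands, and it is why the point is minor. It does not close the HbA1c gap: the glucose tables catch a withdrawn subject only if fasting glucose also qualifies, and the HbA1c rows exclude the baseline group nearest the limit.

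A second reply is that a last on-treatment summary mixes completers' Week 52 values with earlier exit values, much as a pooled 28/ET/EOT visit would. That is true of the arithmetic. The difference is the label: a last-value row says what it is, whereas a row headed Week 52 would not.

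Third, the absence of an end-of-treatment row for laboratory data is read from the text. The mock tables are in a separate document and might include one, but the SAP should state it.

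A reader might go further and infer that the by-visit curve will look flat or improving, or that later means contain only subjects who never crossed. The documents support neither. They give no HbA1c rates, the triggering scheduled value counts at its own visit, and in the assumed scenarios most of a true rise remained visible. Nor does the argument extend to insulin or lipids, since no withdrawal rule acts on them.

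**Conclusion.** The point holds in a limited form. Under Protocol 7.3 with SAP 3.9.2, 6.3 and 7, by-visit HbA1c means after a crossing omit earlier crossers and are shifted downward; glucose follows only indirectly. The direction follows from the rules, but the size does not. With baseline mean 5.4 to 5.6, SD 0.30 to 0.45 and drift +0.1 to +0.2 per year, all assumed, the Week 52 bias is about 0.001 to 0.06 points in level and 0.000 to 0.02 in change from baseline if early-termination samples are kept out of Week 52. If they are filed there, Week 52 is a mixture of visit times, while Weeks 12 to 36 are affected either way.

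It would be tempting to say that the design hides a mean rise in HbA1c. On these inputs it would not do so by itself. The firmer finding needs no assumption: a subject moving from 5.7–6.4% to 6.5% or more is withdrawn for that value and appears in no HbA1c category. This is a low-cost improvement, not a flaw that threatens the study's conclusions.

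**What to change.** In SAP 3.9.2:
- For HbA1c and fasting glucose, summarise the last on-treatment value (using the SAP 6.1 definition) and the worst on-treatment value, each with change from baseline, in all Safety Population subjects with a postbaseline value. Say that the worst value includes unscheduled samples, since the section otherwise excludes them.
- Add a Table 3 row for HbA1c from baseline below 6.5% (or 5.7% to below 6.5%) to any postbaseline value of 6.5% or more.
- State that early-termination samples are kept out of the Week 52 by-visit mean, or shown on a separate line.
- Footnote the by-visit HbA1c table to say that subjects reaching 6.5% are withdrawn under the protocol.

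The cost is a few table rows and a footnote. No new data are needed, and the withdrawal rule stays as it is.
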